9.3.2 Protocol deviations

Important protocol deviations are summarized by category (first timing, then high-level topic), per treatment group and overall on the FAS.

A listing of all protocol deviations (coded term, reported term) by country and site is provided on the SCR.

9.3.3 Analysis sets

Subject membership in the different analysis sets is presented in a listing.

9.4 Analyses of subject characteristics

9.4.1 Demographics

Demographic characteristics [defined in Section 5.2.1] are summarized using descriptive statistics for continuous and categorical data using the FAS. Tables are presented by treatment group and overall. All variables are also presented in a subject data listing based on the SCR.

9.4.2 Baseline disease characteristics

Baseline disease characteristics [defined in Section 5.2.2] are summarized using descriptive statistics for continuous and categorical data using the FAS. Tables are presented by treatment group and overall. All variables are also presented in subject data listings based on the SCR.

9.4.3 Previous and concomitant therapies

Number and percentages of subjects having taken at least one treatment are presented by at least one therapy, ATC class and individual PT within each ATC class (ATC class level 4). All summaries are tabulated by ATC class, and individual PTs within each ATC class, for the FAS, by treatment group and overall. ATC classes are sorted by descending order of frequency. If the frequencies of ATC class are the same, alphabetical order is used. The same rule applies for PTs within ATC class. If the frequencies of ATC class are the same, alphabetical order is used. The same rule applies for PTs within ATC class.

The above described frequencies are summarized by treatment group and overall for the following therapies:

- Treatment concomitant therapies (taken between study treatment start and EOT +15 days)

All therapies taken are reported in one subject listing with all information collected on the eCRF presented, using flags to mark previous, treatment concomitant, and therapies starting after EOT, as well as ongoing at study treatment start using the screened set.

9.5 Analysis of study treatment exposure and compliance

9.5.1 Study treatment exposure and compliance

9.5.1.1 Study treatment exposure

Exposure to study drug [defined in Section 5.3.1.1] is summarized using descriptive statistics for continuous and categorical data using the SAF. In addition, this table displays the overall subject year exposure (sum over all subjects' exposure). Tables are presented by treatment group. All variables are also presented in subject data listings, together with compliance, based on the SAF.

Subjects with at least one interruption as well as duration of interruptions will be summarized by treatment group on the SAF. Subject exposure to study drug is listed. Subjects with > 1 tablet taken on at least one day or maintenance treatment resumed without up-titration after an interruption of > 3 days are flagged.

9.5.1.2 Compliance with study treatment

Compliance with study treatment variables [defined in Section 5.3.1.2] are summarized using descriptive statistics for continuous and categorical data using the SAF. Tables are presented by treatment group. All variables are also presented in subject data listings, together with exposure, based on the SAF.

9.5.2 DMF exposure and compliance

9.5.2.1 DMF exposure during study treatment

Exposure to DMF [defined in Section 5.3.3.1] is summarized using descriptive statistics for continuous and categorical data using the SAF. In addition, this table displays the overall subject year exposure (sum over all subjects' exposure). Tables are presented by treatment group. All variables are also presented in subject data listings based on the SAF.

9.5.2.2 Compliance with DMF during study treatment

Compliance with DMF variables [defined in Section 5.3.3.2] are summarized using descriptive statistics for continuous and categorical data using the SAF. Tables are presented by treatment group. All variables are also presented in subject data listings based on the FAS.

9.6 Analysis of the primary efficacy variable

9.6.1 Hypothesis and statistical model

A generalized linear model with negative binomial distribution for the number of confirmed relapses will be assumed as described in Section 10.1.

Two-sided hypotheses are expressed in terms of the model parameters $\mu_{\text{Ponesimod}}$ and μ_{Placebo} . The primary null hypothesis is that the ARR (μ) does not differ between ponesimod and placebo. The alternative hypothesis is that the ARR differs between ponesimod and placebo.

$$\begin{aligned} H_{0, \text{ARR}}: \mu_{\text{Ponesimod}} - \mu_{\text{Placebo}} &= 0 \\ &\text{vs} \\ H_{1, \text{ARR}}: \mu_{\text{Ponesimod}} - \mu_{\text{Placebo}} &\neq 0 \end{aligned}$$

The null hypothesis will be tested by a two-sided Wald test within the negative binomial regression model [see Section 9.6.2], with a two-sided significance level of 0.05.

9.6.2 Main analysis

The primary statistical analysis will be performed up to EOS on the FAS using a negative binomial (NB) regression model for confirmed relapses, with treatment as a factor and the binary stratification variable for EDSS category ($\text{EDSS} \leq 3.5$ versus $\text{EDSS} > 3.5$) from IRT included in the model. The model also includes an offset variable defined as the log of time on study (in years) from randomization up to EOS. The effect size will be measured by the relative reduction in the model estimated mean ARR for ponesimod compared to placebo including two-sided 95% Wald confidence interval (CIs).

Mean model-based estimates of the ARR (for confirmed relapses), by treatment arm, as well as 95% CIs are presented. A rate ratio comparing ponesimod 20 mg with placebo will be derived from the model including 95% CIs and the corresponding p-value. The dispersion parameter will also be displayed.

Descriptive summary statistics of the number of confirmed relapses as a continuous variable and the number of confirmed relapses in categories (0, 1, 2, 3, 4, ≥ 5), by treatment arm will be presented. The total cumulative number of confirmed relapses, as well as the total cumulative time on study (summed for all subjects) will also be displayed. From the total number of confirmed relapses and the total time on study the raw unadjusted ARR, by treatment arm, will be calculated and summarized.

The fit of the model will be assessed and other distributions such as the Poisson distribution will be considered in case of a lack of fit.

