10.1 Statistical methodology for count data

Count data will be analyzed assuming data is negative binomially (NB) distributed.

A generalized linear model with NB distribution will be assumed.

- t_j denotes the length of observation for subject j .
 Y_j denotes the counts of interest for subject j during t_j .
 μ_j denotes the mean of the NB distribution of Y_j .

The mean for the distribution of the ARR for subject j , denoted by μ_j/t_j , will be modeled by the following equation:

$$\log(\mu_j/t_j) = \mathbf{x}'_j \boldsymbol{\theta}, \text{ i.e., } \log(\mu_j) = \mathbf{x}'_j \boldsymbol{\theta} + \log(t_j), \text{ where}$$

- \mathbf{x}_j is the vector denoting study treatments and covariates for subject j
 $\boldsymbol{\theta}$ is the vector of unknown fixed-model parameters.

The SAS code for the NB model with 95% CI is as follows (considered “draft” until fully validated at analysis stage):

```
proc genmod data=ADREL;
  class Treat Strat Covar;
  model COUNTS = Treat Strat Covar / dist=negbin link=log
  offset = offset;
  lsmeans Treat / cl exp alpha = 0.05 OM;
  estimate 'Ponesimod - Placebo' || Treat 1 -1 / exp alpha = 0.05;
run;
```

The offset variable used will be specified per analysis (e.g., for ARR it is the log-transformed observation time, for total T1 lesions it is the log-transformed number of available MRI scans, ...).

The ‘LSMEANS’ statement will output the mean estimates for each of the treatment arms with 95% Wald CIs; the option OM ensures that the mean is derived for categorical covariates with weights as per observed marginal proportions.

The ‘ESTIMATE’ statement will output the rate ratio of the treatment effect with 95% Wald CIs. The direction of the estimate statement (governed by ‘1 – 1’ or ‘–1 1’) is chosen such that the rate ratio relative to placebo is provided (with rate ratio < 1 indicating ponesimod is better).

The number of covariates / stratification variables included in the model is different from analysis to analysis, and these are described in the respective analysis sections [see Section 9]. Interaction terms might be included in the model, depending on the analysis.

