If the NB distribution is not considered to be appropriate (e.g., due to non-convergence), other distributions such as the Poisson and zero-inflated Poisson will be explored. For the Poisson distribution, a Poisson regression is conducted with model equation identical to the one for the negative binomial regression. The SAS code is as follows (considered “draft” until fully validated at analysis stage):

```
proc genmod data=ADREL;
  class Treat Strat Covar;
  model COUNTS = Treat Strat Covar / dist=poisson link=log
  offset = offset;
  lsmeans Treat / cl exp alpha = 0.05;
  estimate 'Ponesimod - Placebo' || Treat 1 -1 / exp alpha = 0.05;
run;
```

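### The Poisson fallback for the relapse and CUAL models cannot repair negative binomial misfit, and as coded it has no overdispersion correction and drops the stratum weighting

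*SAP*

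**What the plan says.** Section 9.6.1 sets one formal test, a two-sided Wald test in the negative binomial model "with a two-sided significance level of 0.05". Section 9.6.2 carries it out "using a negative binomial (NB) regression model for confirmed relapses", with treatment, the EDSS stratum and a log-time offset. It then adds that fit will be assessed and that "other distributions such as the Poisson distribution will be considered in case of a lack of fit". Section 9.7.3 has the same clause for CUAL, which also reports a rate ratio and p-value.

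Section 10.1 words the trigger differently: "If the NB distribution is not considered to be appropriate (e.g., due to non-convergence), other distributions" come into play. The candidates also differ: "other distributions such as the Poisson and zero-inflated Poisson will be explored". Only Poisson is coded: "model COUNTS = Treat Strat Covar / dist=poisson link=log", with the same terms and offset as the negative binomial model. There is no scale option and no `REPEATED` statement.

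The negative binomial code requests arm means by "lsmeans Treat / cl exp alpha = 0.05 OM", and the text explains that `OM` weights categorical covariates by their observed proportions. The Poisson code has only "lsmeans Treat / cl exp alpha = 0.05".

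No fit statistic, threshold or order of alternatives is given, and section 9.6.3 plans no sensitivity analysis.

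**The concern.** The plan offers a special case of the negative binomial model as the remedy when that model does not fit. If the misfit comes from variation that the negative binomial fails to capture, Poisson captures less of it and shrinks the standard errors. The choice would be made after the data are seen, and no pre-specified alternative result would stand beside the replacement. At stake is the type I error of the only formally tested endpoint, together with the width of its interval. The same clause governs the CUAL rate ratio. Separately, the missing `OM` means that the arm-level rates displayed from the two models would be standardized to different stratum mixes.

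**Working it through.** **Nesting.** The negative binomial variance is μ + kμ², and k = 0 gives Poisson. Section 10.1 keeps the linear predictor and offset the same, so Poisson can at best equal the negative binomial likelihood.

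**Inputs from the SAP.** 136 randomized subjects (section 2), 1:1 allocation, two-sided 0.05, and a model with treatment, binary EDSS stratum and log-time offset. Enrolment from March 2017 and termination on 26 November 2019 (section 1) bound follow-up at about 2.7 years plus close-out.

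**Assumptions, because the SAP gives no figures.** All 136 subjects analysed, ARR 0.2 to 0.4, k from 0 to 2, follow-up uniform on 0.1 to 2.75 years, 20% with EDSS > 3.5. The SAP states no error rate for the fallback, so there is no figure to reproduce.

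**Analytic check.** The Poisson variance of the log rate ratio is too small by about 1 + k·ARR·E[t²]/E[t].

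- E[t] = (0.1 + 2.75)/2 = 1.425
- E[t²] = (2.75³ − 0.1³)/(3 × 2.65) = 2.616
- E[t²]/E[t] = 1.836
- At ARR 0.3 and k = 1, the inflation is 1 + 0.3 × 1.836 = 1.55
- True size = 2(1 − Φ(1.96/√1.55)) = 11.6%

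The same formula gives 8.3% at k = 0.5 and 17.6% at k = 2.

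**Simulation under the null**, 1,500 trials per setting, Monte Carlo standard error about 0.6 to 1.0 point. Entries are the two-sided type I error of plain Poisson, with the negative binomial in brackets:

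| ARR | k = 0 | k = 0.5 | k = 1 | k = 2 |
|---|---|---|---|---|
| 0.2 | 3.7% (3.5%) | 6.4% (4.7%) | 7.5% (4.7%) | 13.1% (5.6%) |
| 0.3 | 4.0% (3.9%) | 7.4% (5.5%) | 11.1% (5.9%) | 15.9% (5.3%) |
| 0.4 | 4.9% (4.7%) | 10.2% (6.2%) | 13.9% (6.7%) | 19.9% (5.5%) |

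At ARR 0.3 the Poisson standard error averages 0.91, 0.83 and 0.73 of the negative binomial one for k = 0.5, 1 and 2, so log-scale intervals are about 9%, 17% and 27% too narrow. Over the whole table, Pearson-scaled Poisson gives 4.4–7.5% and sandwich variance 4.6–7.3%.

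**Poisson used only when the estimated dispersion is zero.** With true k = 0 this happens in 61–65% of trials, and Poisson size in them is 3.2–5.2%. It also happens by chance under overdispersion. At ARR 0.2 it occurs in 25% of trials for k = 0.5 (size 6.2%) and in 10% for k = 1 (7.1%). At ARR 0.3 and k = 0.5 it occurs in 14% (5.8%). A second run of 3,000 trials per setting (ARR 0.25, follow-up 0.3 to 2.8 years) gave 4.8%, 6.5% and 7.1% for k = 0, 0.5 and 1. The other settings had 90 or fewer such trials. They scatter widely (for example 10.0% on 90 trials, standard error about 3 points) and settle nothing.

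**Missing `OM`.** Let p be the proportion with EDSS > 3.5, and R the relapse rate in that stratum divided by the rate in the other. Equal weights multiply the displayed arm mean by R^(0.5 − p) relative to observed weights. With p = 0.2 and stratum rates 0.2 and 0.4 (assumed), `OM` gives exp(0.8 ln 0.2 + 0.2 ln 0.4) = 0.230 and equal weights give √(0.2 × 0.4) = 0.283, which is 23% higher. With R = 1.5 the excess is 1.5^0.3 − 1 = 13%. With p = 0.5 or R = 1 there is none. Without a treatment-by-stratum interaction the factor is the same in both arms and cancels from the rate ratio.

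**The case against.** A reader might infer that the plan switches to Poisson whenever fit is poor and that the primary test is therefore invalid. The text does not go that far. Alternatives are to be considered or explored, zero-inflated Poisson is also named, and section 9.6.1 places the test inside the negative binomial model. The only example trigger in section 10.1 is non-convergence. A typical cause of that is dispersion at or near zero, where plain Poisson is close to adequate. The table above applies Poisson to every simulated trial, so it is not the error rate of the planned procedure. This stands, and it limits the size of the claim. It does not rescue the lack-of-fit clause, which names Poisson for the one trigger it cannot cure.

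A reader might also infer far larger errors for CUAL. Null simulations at assumed lesion rates of 1.5 per year with dispersion 1.5, and 2.5 per year with dispersion 2, give about 39% and 54–56% for plain Poisson. These are not a fair measure of the plan. The data were generated as exactly negative binomial, so that model was correct, and a zero-dispersion trigger arose in none of 3,000 trials at either setting. Sections 9.1.1 and 9.7 also make CUAL exploratory.

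Further mitigation is real. The code is labelled draft, the trial stopped at 136 of about 600 planned subjects and is reported synoptically, and section 9.6.2 displays the dispersion parameter, the relapse counts by category and the raw rates. The `OM` omission touches only displayed arm means.

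**Conclusion.** The point holds as a conditional defect. Poisson cannot remedy lack of fit of the negative binomial model, and the only coded fallback has no protection against overdispersion. Used regardless of trigger at ARR 0.2–0.4 with 136 subjects, it gives about 6–10% type I error at dispersion 0.5, 8–14% at 1 and 13–20% at 2. At dispersion 0 it keeps its level. Used only because the estimated dispersion is zero, it gives about 5–7%, on limited numbers of trials. Rates, dispersion, follow-up and stratum mix are all assumed; the nesting argument and the content of the code are not.

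The `OM` omission contradicts the SAP's own explanation of how arm means are weighted. Its size cannot be fixed from the SAP. It leaves the rate ratio, its interval and the p-value unchanged.

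**What to change.** - In sections 9.6.2 and 9.7.3, delete the clause that offers Poisson for lack of fit.
- In section 10.1, allow Poisson only if the negative binomial model does not converge or its dispersion is estimated as zero. Keep the same terms and offset.
- Fix one variance correction in advance, either a sandwich variance through `REPEATED SUBJECT=` or Pearson scaling. The two performed about equally above.
- Add `OM` to the Poisson `LSMEANS` statement.
- State that any zero-inflated Poisson fit is exploratory and does not replace the primary rate ratio. Its count-part treatment coefficient describes only subjects outside the structural-zero class, which is not the contrast of section 9.6.1.

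The cost is two deleted clauses, a few lines in section 10.1, one added statement or option for the variance, and one restored option. The downside is slightly wider intervals when the fallback is used.

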9.6.3 Sensitivity analyses to main analysis

No sensitivity analyses are planned.

9.6.4 Supplementary analyses

9.6.4.1 ARR based on all relapses up to EOS on the FAS

Same analysis as for the main analysis, but with number of all relapses up to EOS as a response variable. All other aspects of the model are as per the main analysis. This analysis is described to check the consistency of the treatment effect on all relapses and that no bias was introduced in the confirmation of relapses.

A listing of relapses and a listing for number of relapses will be prepared on FAS.

9.6.5 Subgroup analyses

No subgroup analyses are planned.

9.7 Analysis of the secondary efficacy variables

All analyses of secondary efficacy variables are considered to be exploratory.

9.7.1 Analysis of time to 12-week CDA

Time to first confirmed 12-week CDA up to EOS will be summarized on the FAS in a table including, number of subjects with event / censored, Kaplan-Meier estimates (unstratified) and corresponding CI (anticipated timepoints: 12, 24, ..., 156 weeks), and median (as well as 25th and 75th percentiles) of the survival function together with CIs.

A listing of 12-week CDA data will be prepared.

9.7.1.1.1 Handling of missing data

See variable derivation in Section 5.4.2.1.

9.7.2 Time to first confirmed relapse

Time to first confirmed relapse will be summarized on the FAS in a table including, number of subjects with event / censored, Kaplan-Meier estimates (unstratified) and corresponding CI (anticipated timepoints: 12, 24, ..., 156 weeks), and median (as well as 25th and 75th percentiles) of the survival function together with CIs. A graphical display presenting a Kaplan-Meier plot

(unstratified) going upward is presented including CIs at specific timepoints. Intervals will be displayed up to the time point where at least 10% of subjects are still at risk.

Time to first confirmed relapse data will be listed using the FAS.

9.7.3 Analysis of cumulative unique active lesions (CUAL) from baseline up to EOS

The main analysis of the secondary endpoint CUAL will be performed on the FAS using a negative binomial regression model: response variable is the cumulative number of CUALs up to EOS, with treatment as a factor and the IRT stratification variable for EDSS ($EDSS \leq 3.5$ versus $EDSS > 3.5$) included in the model. The model also includes an offset variable defined as the log of the time up to last MRI (in years) considered for analysis.

Mean model-based estimates of the number of CUALs per subject per year will be provided by treatment group, as well as 95% Wald CIs. A rate ratio comparing ponesimod 20 mg with placebo will be derived from the model including 95% Wald CIs and the corresponding p-value. The dispersion parameter will also be displayed.

The fit of the model will be assessed and other distributions such as the Poisson distribution will be considered in case of a lack of fit.

Descriptive summary statistics of the number of CUALs from baseline up to EOS will be presented for continuous data and frequency per categories (0, 1–5, 6–10, 11+) anticipated. The total number of CUALs as well as the total cumulative time up to the last MRI scan (summed for all subjects) will also be displayed. From the total number of CUALs and the total cumulative time to the last MRI scan the raw number of CUALs per year will be calculated and summarized.

A listing of CUAL data will be presented.

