- **Number of relapses in the year prior to study entry**, as reported in the corresponding question on the ‘MS History - Relapse’ eCRF (i.e., not based on recorded onset dates of previous relapses). Data collected at re-screening overwrites the initially entered data.
- **Number of relapses in the 2 years prior to study entry** as reported in the corresponding question on the ‘MS History - Relapse’ eCRF (i.e., not based on recorded onset dates of previous relapses). Data collected at re-screening overwrites the initially entered data.
- **Prior MS treatment other than DMF (yes/no)** (‘yes’ if any MS treatment recorded on then ‘MS Specific Treatment History’ eCRF form or as prior concomitant medications on the

‘Study-concomitant therapy - Disease-modifying treatment for MS’ eCRF; otherwise ‘no’ if no such medications are recorded).

- **Months on DMF at screening** defined as [Date of screening – DMF start date] in days / 30.4375. DMF start date is defined as the earliest DMF start date documented in the Drug Log – DMF eCRF. In case of partially missing DMF start date, the start date is imputed to the latest possible date, see Section 12.1.1 for full details.
- **Relapses in the previous 6 months prior to study entry while on treatment with DMF (0, 1, ≥ 2)** number of relapses recorded in the 6 months prior to date of screening based on recorded onset dates of previous relapses (‘MS History – Relapse’ eCRF form) and recorded start/end dates of DMF treatment.
- **Presence of T1 Gd+ lesions (yes/no) in the previous 12 months prior to study**, as provided by sites (yes/no) - (‘MS history - MRI’ eCRF form).
- **Presence of T1 Gd+ lesions (yes/no)** on baseline MRI scan as provided by the MRI central reading.
- **Number of documented T1 Gd+ lesions** on baseline MRI scan as provided by the MRI central reading.
- **Presence of new or enlarging T2 (yes/no) in the previous 12 months prior to study**, as provided by sites (yes/no) - (‘MS history - MRI’ eCRF form).
- **Volume of T2 lesions** on baseline MRI scan as provided by the MRI central reading.
- **Smoking status** (Current smoker, Former smoker, Never smoked), taken from ‘Smoking status’ eCRF.

Note: For re-screened subjects, information for baseline characteristics ‘at screening’ is taken from the last Re-screening Visit, if available, instead of the Screening Visit.

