5.4.2.3.1 Derivation details

The central reader provides the ‘Number of new T1 Gd+ enhancing lesions’ (variable T1GdNew_R) and ‘Number of new T2 lesions without Gd enhancement’ (variable T2New_R) at a visit as compared to the last scheduled MRI scan (with premature EOT visit being considered a scheduled MRI). At the first scheduled post-baseline visit comparison is made to baseline (with baseline defined as the Baseline Visit 2, or Visit 2 - 2nd attempt if available [see Section 5.4.3] for details and a rationale).

Cumulative CUAL from baseline to EOS is derived as the sum of ‘Number of new T1 Gd+ enhancing lesions’ and ‘Number of new T2 lesions without Gd enhancement on T1’ across all post-baseline MRI visits up to up to EOS irrespective of whether a visit is conducted during PTOP or not.

As only the number of new lesions as compared to the last scheduled visit is recorded by the central reader, lesions are not expected to be double counted when summing over scheduled visits.

In the rare event that the baseline MRI visit is conducted after randomization date, the variable is derived in the same way, i.e., based on the nominal visit. Note that effectively the derived variable then covers a period starting slightly after randomization. If the baseline MRI is missing, new or enlarging T2 lesions as compared to baseline cannot be assessed and consequently the endpoint is considered missing. The baseline MRI is considered missing if presence of T1 Gd+ lesions at baseline is missing.

For subjects with at least one unscheduled post-baseline MRI scan, care needs to be taken in the derivation to avoid double counting of lesions and the following algorithm applies:

- If a subject has an unscheduled MRI which is the last available MRI in the time period considered: Include that last unscheduled MRI when deriving CUAL in the same way as for scheduled visits.
- If a subject has an unscheduled MRI which is not the last available MRI for the subject: Do not include that unscheduled MRI. Rationale: New / enlarging lesions at the unscheduled MRI as well as at the later scheduled MRI are reported in reference to the previous scheduled visit. Including both may result in double counting.

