9.8 Analysis of exploratory MRI efficacy variables

9.8.1 Number of CUALs

The cumulative number of CUALs from baseline up to Weeks 24, 48, 72, 96 and EOT will be analyzed on the FAS using a negative binomial regression model: response variable is the cumulative number of CUALs up to each timepoint, with treatment as a factor and EDSS category (IRT) as a covariate, and the log of the time up to last MRI scan for the timepoint (in years) as an offset. Mean model-based estimates for the number of CUALs per subject per year, rate ratio, and corresponding 95% CIs will be presented.

The cumulative number of CUALs from baseline up to each timepoint will be summarized descriptively using the FAS. The total number of CUALs as well as the total cumulative time up to the last MRI scan at the timepoint (summed for all subjects) will also be displayed. From the total number of CUALs and the total cumulative time to the last MRI scan the raw number of CUALs per year will be calculated and summarized.

CUAL data will be listed on the FAS.

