9.8.2 Number of T1 Gd+ lesions

The cumulative number of T1 Gd+ lesions up to Weeks 24, 48, 72, 96, EOT and EOS will be analyzed on the FAS using a negative binomial regression model, with the cumulative number of T1 Gd+ lesions up to the timepoint as the response variable, treatment as a factor, EDSS stratification category as a covariate, and the log of the number of included scans up to the timepoint as an offset. Mean model-based estimates for the number of T1 Gd+ lesions per subject per scan, rate ratio, and corresponding 95% CIs will be presented.

The cumulative number of T1 Gd+ lesions from baseline up to each timepoint will be summarized descriptively using the FAS. The total number of T1 Gd+ lesions as well as the total number of included scans (summed for all subjects) will also be displayed. From the total number of T1 Gd+ lesions and the total number of included scans the raw number of T1 Gd+ lesions per scan will be calculated and summarized. For the number of T1 Gd+ lesions from baseline up to EOS the frequency per category will also be presented (anticipated categories: 0, 1, 2, 3, 4+).

Descriptive summary statistics of the number of T1 Gd+ lesions at each scheduled visit will also be presented.

T1 Gd+ lesion data will be listed on the FAS.

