9.8.3 Number of new or enlarging T2 lesions

The cumulative number of new or enlarging T2 lesions up to Weeks 24, 48, 72, 96, EOT and EOS will be analyzed on the FAS using a negative binomial regression model as described above in Section 9.8.1 for number of CUALs, with the cumulative number of new or enlarging T2 lesions up to the timepoint as the response variable.

The cumulative number of new or enlarging T2 lesions from baseline up to each timepoint will be summarized descriptively using the FAS. The total number of new or enlarging T2 lesions as well as the total cumulative time up to the last MRI scan at the timepoint (summed for all subjects) will also be displayed. From the total number of new or enlarging T2 lesions and the total cumulative time to the last MRI scan the raw number of new or enlarging T2 lesions per year will be calculated and summarized. For the number of new or enlarging T2 lesions from baseline up to EOS the frequency per category will also be presented (anticipated categories: 0, 1, 2, 3, 4+).

Descriptive summary statistics of the number of new or enlarging T2 lesions at each scheduled visit will also be presented.

T2 lesion data will be listed on the FAS.

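### The MRI lesion models adjust only for the EDSS stratum although centrally read baseline T1 Gd+ status is available; the models are valid but may give up some precision with 136 subjects

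*SAP*

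**What the plan says.** The count models all have the same structure:

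- **CUAL up to EOS (SAP 9.7.3, secondary):** "with treatment as a factor and the IRT stratification variable for EDSS", with log time to last MRI as offset.
- **CUAL by timepoint (9.8.1, Number of CUALs):** "with treatment as a factor and EDSS category (IRT) as a covariate", with the same type of offset.
- **T1 Gd+ lesions (9.8.2, Number of T1 Gd+ lesions):** "treatment as a factor, EDSS stratification category as a covariate, and the log of the number of included scans" as offset.
- **New or enlarging T2 lesions (9.8.3):** "using a negative binomial regression model as described above in Section 9.8.1 for number of CUALs".
- **Primary ARR (9.6.2):** "with treatment as a factor and the binary stratification variable for EDSS category", with log time on study as offset.

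Section 5.2.2 defines presence and number of T1 Gd+ lesions "on baseline MRI scan as provided by the MRI central reading", and also "Number of relapses in the year prior to study entry". Section 9.4.2 uses these variables only in descriptive tables and listings. Section 10.1 leaves the choice of covariates to the individual analysis sections, and none of them names one beyond EDSS. On missing baseline scans, 5.4.2.3.1 says for CUAL: "The baseline MRI is considered missing if presence of T1 Gd+ lesions at baseline is missing"; the endpoint is then missing. Section 5.4.3.3 has the same rule for T2. Section 5.4.3.2 has none for T1 Gd+.

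**The concern.** EDSS measures disability, whereas the MRI endpoints count new inflammatory lesions. Baseline Gd+ status is closer to those endpoints than the EDSS stratum is. Randomization was stratified by EDSS only (section 2), so Gd+ status is balanced only by chance. Section 4.2 records that protocol version 6 added MRI-based alternatives to the disease-activity entry criterion, so subjects could qualify by different kinds of activity.

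Recruitment stopped at 136 of about 600 planned subjects, which leaves the analysis as one of the few places where precision can still be gained. The CUAL analysis still reports a rate ratio, a confidence interval and a p-value. If baseline Gd+ status predicts lesion counts, leaving it out makes that interval wider than necessary and leaves any chance imbalance in the single reported estimate.

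**Working it through.** **What the SAP supplies.** 136 randomized, 1:1, so about 68 per arm. It gives no lesion rate, dispersion, effect size, Gd+ prevalence or prognostic strength, and no power calculation to reproduce. Every such value below is an assumption.

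**1. Why MRI counts can gain and relapse counts hardly can.** For a negative binomial model with log link,

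SE² = [(1/(μ₀t) + k) + (1/(μ₁t) + k)] / n,

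with n = 68 per arm. A covariate that explains share R of the between-subject dispersion replaces k by k(1 − R). Mean follow-up is taken as t = 2.7/2 + 86/365.25 = 1.585 years (uniform accrual from March 2017 to November 2019, wind-down of 56 + 30 days, no dropout).

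- *CUAL*, 2 per year on placebo, rate ratio 0.5, k = 2: 1/3.171 + 1/1.585 = 0.946. SE = √[(0.946 + 4)/68] = 0.270. With R = 0.25, SE = √[(0.946 + 3)/68] = 0.241, which is 11% lower.
- *ARR*, 0.3 per year on placebo, rate ratio 0.6, k = 1: 1/0.476 + 1/0.285 = 5.607. SE = √[(5.607 + 2)/68] = 0.334. With R = 0.25, SE = √[(5.607 + 1.5)/68] = 0.323, which is 3% lower.

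Over wider ranges at R = 0.25, the SE falls by 7 to 12% for CUAL (1 to 4 per year, k 1 to 3) and by 1 to 6% for ARR (0.2 to 0.4 per year, k 0.5 to 2). With few relapses the Poisson term dominates, and a covariate cannot reduce it.

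**2. Gain from baseline Gd+ yes/no in the CUAL model.** Trials of 136 subjects were simulated with 33 to 35% Gd+ at baseline and dispersion 1.2 to 1.5, and fitted with and without the covariate:

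| Lesion rate, Gd+ vs not | Fall in model-based variance of log rate ratio | CI width ratio |
|---|---|---|
| 1.5 times | about 1% | √0.99 = 0.99 |
| 2 times | about 5% | √0.95 = 0.97 |
| 3 times | about 12% | √0.88 = 0.94 |
| 4 times | 17 to 19% | √0.83 to √0.81 = 0.91 to 0.90 |

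With a non-prognostic covariate the variance ratio was about 1.00. In a separate simulation of CUAL with a continuous covariate of no prognostic value, the median SE moved from 0.280 to 0.281.

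**3. A second measure.** The model-based variance sets the printed interval. The spread of the estimates across simulated trials can fall by more: with 30% Gd+, dispersion 1.5, rate ratio 0.6 and 2 lesions per year, the empirical variance ratios were 1.00, 0.91 and 0.80 at 1.5, 2 and 3 times the rate. The direction is the same, and the size again depends on the assumed multiplier.

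**4. Chance imbalance.** With 33% Gd+, the SD of the difference between arms is √(2 × 0.33 × 0.67/68) = 0.081. A gap of at least 10 points then has probability of about 21%. If Gd+ subjects have 3.5 times the rate, a gap of 38% against 28% shifts the unadjusted rate ratio by (1 + 0.38 × 2.5)/(1 + 0.28 × 2.5) = 1.95/1.70 = 1.15.

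**The case against.** The strongest reply is that nothing here is wrong. Adjusting for the stratification factor matches the randomization, and chance imbalance is part of what the confidence interval covers. A reader might infer bias or a faulty model; the documents do not support that, and this part of the reply stands.

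The reply also holds on size. A reader might take baseline Gd+ to be a strong predictor, but the SAP says nothing about its strength. Sections 4.1 and 5.4.2.3 expect CUAL to be driven mainly by new T2 lesions, so baseline Gd+ is the direct baseline counterpart of the T1 Gd+ endpoint only. With 3 to 4 times the lesion rate assumed, one simulation gave empirical variance reductions of 22 to 36%. A reader might turn these into 28 to 56% more subjects (1/0.78 = 1.28; 1/0.64 = 1.56). That is the favourable end. The same runs raised power only from 57.5 to 65.0%, 52.8 to 66.3% and 47.5 to 52.8%. Since the required n scales with (1.96 + z for power)², these equal about 19%, 37% and 15% more subjects: (2.345/2.149)², (2.381/2.030)² and (2.030/1.897)².

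A reader might also want the primary ARR model changed. The gain is too small for that, and 14 to 73 of 400 simulated ARR data sets per scenario were dropped for failed or unstable fits. Section 4.2 also records that the primary analysis was modified after regulatory review.

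Finally, the secondary endpoints are exploratory (9.1.1, 9.7) and the report is a synoptic CSR, so little hangs on these p-values. That limits the importance of the point. It does not remove it, because rate ratios with intervals will still be reported and the change costs almost nothing.

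**Conclusion.** The point holds as a modest efficiency improvement for the CUAL, T1 Gd+ and T2 models. The calculations for CUAL suggest roughly 0 to 5% lower model-based variance if Gd+ subjects have 1.5 to 2 times the lesion rate, and about 10 to 20% (intervals about 6 to 10% narrower) if 3 to 4 times. The assumptions are about one third Gd+ at baseline and dispersion of 1.2 to 1.5. T1 Gd+ and T2 were not simulated separately. The facts about model content are certain; the size of the gain is not. With a log link the rate ratio is collapsible, so a main-effect covariate leaves the target of estimation unchanged. For ARR the expected gain is about 1 to 6% of the SE if 25% of the dispersion is explained, which does not justify touching the primary model.

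**What to change.** Before unblinding:

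1. In 9.7.3 and in the CUAL, T1 Gd+ and T2 models of 9.8.1 to 9.8.3, add presence of T1 Gd+ lesions on the baseline scan (yes/no, central reading) as a covariate. Fix this one form in advance. Keep the EDSS stratum and the present offsets.
2. In 5.4.3.2 or 9.8.2, state how a missing baseline Gd+ value is handled in the T1 Gd+ model, for example by the rule already used for CUAL and T2.
3. Leave 9.6.2 as written. At most, add a pre-specified supplementary ARR model in 9.6.4 with prior-year relapses as a covariate and a rule for missing values.

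If the change is made after unblinding, label the adjusted models post hoc.

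The cost is one model term and a few lines of SAP text. No subject is lost from the CUAL or T2 models, because those endpoints are already missing when baseline Gd+ presence is missing. The T1 Gd+ model could lose subjects, depending on the rule chosen in step 2.
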